Full study protocol and statistical analysis plan

Official Title of the study:

Analysis of maternal plasma/urine/hair magnesium and vanadium levels in preeclampsia

Date of the document:

May 2020.

Contents:

1. Participant Flow
2. Baseline Characteristics
3. Outcome Measures
4. Endpoints of the study
5. Limitations and Strengths
6. Certain Agreements
7. Results Point of Contact

1. Participant Flow

Recruitment Details

This observational case-control study will be conducted at the Department of Obstetrics and Gynecology, Cengiz Gokcek Public Hospital, Gaziantep, Turkey, between May 2020 and February 2021. The protocol was approved by the Ethics Committee for Clinical Research of Gaziantep University (reference no: 2020/130). The study strictly will be adhered to the principles of the Declaration of Helsinki. All subjects will be included in the study gave oral and written informed consent. Two-hundred ten women will be enrolled in the study in two groups.

The investigators included subjects consisted of women with a singleton pregnancy who were diagnosed as having late-onset preeclampsia between 34+0 and 41+0 weeks of gestation. Pregnant women with uncomplicated pregnancies were randomly selected to serve as controls. Other participants with healthy volunteer women as control non-pregnant group. The study population will have consisted of 70 late-onset preeclampsia patients as a study group, 70 participants with normal pregnancies as control pregnant group and 70 participants with healthy volunteer women as control non-pregnant group. All participants included in the study gave oral and written informed consent.

Pre-assignment Details

The authors firstly were assessed the recruited people to ensure meeting the inclusion and exclusion criteria. The inclusion criteria were made according to the official documents.

Arm/Group Information *

There are three groups in the study.

Arm/Group Title *

Preeclampsia group

Control pregnant group

Control non-pregnant group

2. Baseline Characteristics

To detect significant difference between groups according to variable with a moderate effect size (Cohen's $d = 0.5$), minimum required sample size was estimated as 63 for each group ($\alpha=0.05$, $1-\beta=0.80$). Power analysis was performed by using G power package version 3.1. SPSS for Windows 22.0 and Medcalc programs will be used for statistical analysis. $p<0.05$ will be accepted as statistical significance.

3. Outcome Measures

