The primary outcome in these analyses will be compare magnesium and vanadium levels in LOPE group and the control groups. The secondary outcome will be compare the magnesium and vanadium levels in mild LOPE group and severity LOPE group. Tertiary outcome will be compare the magnesium and vanadium levels in SGA group and non-SGA group. Venous blood sampled from the antecubital veins for measuring plasma concentration of cadmium, lead and vanadium levels. The three metals (cadmium, lead and vanadium) were measured using inductively coupled plasma-mass spectrometry (Thermo Scientific ICAPQc, USA).

4. Endpoints of the study:

The primary outcome in these analyses will be compare magnesium and vanadium levels in LOPE group and the control groups. The secondary outcome will be compare the magnesium and vanadium levels in mild LOPE group and severity LOPE group. Tertiary outcome will be compare the magnesium and vanadium levels in SGA group and non-SGA group.

5. Limitations and strengths:

Because our study is observational, we could not eliminate the possibility of unmeasured and/or residual confounding of the reported associations. . These metals will be measured blood, urine and

hair samples. So, these measurements may not reflect the metals exposure levels only recent exposure and will reflect before and during pregnancy.

6. Certain Agreements

This work will be supported by the Scientific Research Project Fund of Yozgat Bozok University.

7. Results Point of Contact

Corresponding Author: [name], Department of Obstetrics and Gynecology, Cengiz Gokcek Women's and Children's Hospital, Gaziantep, Turkey, [contact]

Address: [name]

GSM: [contact]

[contact]

[contact]

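### The tertiary outcome tests fetal growth only as SGA v non-SGA; if the relation with metal level is roughly linear, a weight-for-gestational-age z-score would have clearly more power

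*Combined protocol and SAP*

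**What the plan says.** Section 3 (Outcome Measures) gives the tertiary outcome as "Tertiary outcome will be compare the magnesium and vanadium levels in SGA group and non-SGA group", and Section 4 (Endpoints of the study) repeats it. This is the plan's only analysis of fetal growth.

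The plan does not define SGA, name a growth chart, give an expected SGA proportion, name a test, or say that weight and gestational age at delivery will be kept as values. It also does not say whether the comparison is made within the preeclampsia group or across all pregnant women. Section 1 enrols "70 late-onset preeclampsia patients as a study group, 70 participants with normal pregnancies as control pregnant group", so either 70 or at most 140 women can contribute.

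The only sample-size statement is in Section 2. It is made "with a moderate effect size (Cohen's $d = 0.5$), minimum required sample size was estimated as 63 for each group", at 80% power and a 0.05 significance level. It is not tied to the SGA comparison.

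**The concern.** SGA (small for gestational age) is assigned by comparing a fetal or birth weight, at a given gestational age, with a reference cut-off. A two-group comparison then treats a baby just above the cut like a very large one, and a baby just below it like a severely small one. It usually also produces unequal groups. At 10-30% SGA there would be 7 to 21 SGA babies among 70 women, or 14 to 42 among 140.

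Section 2 sizes the study for at least 63 women in each of two compared groups. Seventy women cannot supply two such groups. With 140, they can only if the SGA proportion lies between 63/140 = 45% and 77/140 = 55%. So the sample-size statement does not cover this outcome except at a proportion well above the 10-30% assumed here.

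A graded relation between metal level and fetal growth could therefore go undetected, although the measurements behind the SGA label would probably have shown it.

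**Working it through.** **Inputs from the documents:** 70 or at most 140 women (Section 1); d = 0.5, significance level 0.05, power 0.80, 63 per group (Section 2).

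**Assumed, because the documents are silent:** SGA proportion p of 10-30% (5% and 50% shown as extremes); a normal z-score linearly related to metal level; two-sided tests; correlation r = 0.30, with 0.24 as a sensitivity value.

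**1. The plan's own figure.** n per group = 2(1.960 + 0.842)²/0.5² = 62.8, so 63. This reproduces Section 2 with a two-sided normal approximation; the t-test version gives 64.

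**2. Information kept by the cut.** The fraction kept is φ(z_p)²/[p(1−p)], where z_p is the normal quantile at p and φ is the normal density.

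| SGA proportion | φ(z_p) | Kept | Lost | 70 women count as |
|---|---|---|---|---|
| 10% | 0.1755 | 0.0308/0.09 = 0.342 | 66% | 24 |
| 20% | 0.2800 | 0.0784/0.16 = 0.490 | 51% | 34 |
| 25% | 0.3178 | 0.1010/0.1875 = 0.539 | 46% | 38 |
| 30% | 0.3477 | 0.1209/0.21 = 0.576 | 42% | 40 |

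At 5% SGA the loss is 78%. At a 50% split, the most favourable cut, it is 36%.

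**3. What r = 0.30 means as a group difference.** The difference in SD units is r·φ(z_p)/[p(1−p)]. At 20% SGA it is 0.30 × 0.2800/0.16 = 0.525. At 25% it is 0.30 × 0.3178/0.1875 = 0.508. Both are close to the 0.5 used in Section 2.

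**4. Power.** By Fisher's transformation, power = Φ(atanh(ρ)·√(n−3) − 1.96), with ρ = r for the z-score and ρ = r·√(fraction kept) for the split.

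- z-score, n = 70: 0.3095 × 8.185 − 1.96 = 0.573, power 72%.
- Split at 20%, n = 70: ρ = 0.30 × 0.700 = 0.210; 0.2132 × 8.185 − 1.96 = −0.215, power 41.5%.
- z-score, n = 140: 0.3095 × 11.705 − 1.96 = 1.663, power 95%.
- Split at 20%, n = 140: 0.2132 × 11.705 − 1.96 = 0.535, power 70%.

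Simulation with the t-test (20,000 replicates) agrees. For the split it gives 42% and 45% at 20% and 25% SGA with 70 women, and 71% and 75% with 140.

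**5. A weaker relation.** At r = 0.24:

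| Women | z-score | Split, 10% SGA | Split, 20% SGA | Split, 30% SGA |
|---|---|---|---|---|
| 70 | 52% | 21% | 28% | 33% |
| 140 | 82% | 38% | 51% | 58% |

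**6. A threshold relation.** Here metal level shifts by 0.5 SD only below the SGA cut (simulated, 4,000 runs per setting).

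| Women | SGA | z-score | Split |
|---|---|---|---|
| 70 | 10% | 11% | 24% |
| 70 | 30% | 29% | 46% |
| 140 | 10% | 17% | 42% |
| 140 | 30% | 53% | 78% |

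The ranking reverses. None of the figures for 140 women includes a LOPE/control term.

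**The case against.** SGA is a recognised clinical category, and asking whether metal levels differ in SGA pregnancies is a legitimate question. Nothing in the plan says that the investigators expect a gradient across all birth weights. If the true pattern is a step at the cut, replacing the planned test would remove the better one. This objection stands, and it is why the SGA comparison should remain as a supporting test rather than a descriptive summary.

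Four stronger readings are tempting, but the documents do not support them:

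- *That this study will lose 42-66% of its information.* The figure depends on an SGA proportion and a linear-normal model, neither of which is in the plan.
- *That the planned test will usually miss a moderate effect.* At r = 0.30 this holds for 70 women, where power is below 50% at 10-30% SGA. It fails for 140 women at 20-30% SGA, where power is about 70-77%.
- *That the plan claims 80% power here, or that d = 0.5 was set for SGA.* Section 2 refers to group differences in general.
- *That the z-score certainly already exists.* Assigning SGA needs a weight and a gestational age, so this is a reasonable inference. But the plan does not say how SGA is assigned, and only a yes/no label might be recorded.

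Pooling is a further caution. If both pregnant groups are combined, preeclampsia may relate both to metal level and to fetal growth, so an unadjusted slope could partly reflect the LOPE-control difference.

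**Conclusion.** The concern holds in conditional form. The plan's only fetal-growth analysis is a dichotomy. Under a linear relation with a normal z-score, no SGA proportion brings the loss below 36%, and at an assumed 10-30% it is 42-66%. At a difference of about 0.5 SD and 20-25% SGA, the z-score gains roughly 27-30 percentage points of power with 70 women (72% against 42-45%) and 20-24 points with 140 (95% against 71-75%).

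The advantage is not unconditional, since a pure threshold effect favours the split. It is also no guarantee of adequate power: the z-score reaches only 52% with 70 women at r = 0.24. As this is the third-ranked outcome of an observational study, the change is worthwhile because it is cheap. It has no bearing on the primary comparison.

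**What to change.** In Sections 3 and 4:

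- Define SGA and name the reference chart.
- State whether the tertiary analysis uses the 70 LOPE women or all 140 pregnant women.
- Make the main tertiary analysis a linear regression of each metal level (transformed if skewed) on the birth-weight-for-gestational-age z-score from that same chart, with a LOPE/control term if the groups are pooled.
- Report the slope with its 95% confidence interval, and check linearity, for example with a quadratic term.
- Keep SGA v non-SGA as a supporting comparison, reporting the difference with its 95% confidence interval.

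The cost is a few sentences of text and one extra model per metal (for each sample type analysed). No new visits or assays are needed. Weight and gestational age must be recorded as values, which assigning SGA already requires. The downside is a linearity assumption in the main analysis, which the linearity check and the retained SGA comparison are there to cover.

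### Section 3 lists cadmium, lead and vanadium for assay, while the title and all three outcomes name magnesium and vanadium, so magnesium has no stated assay

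*Combined protocol and SAP*

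**What the plan says.** The official title reads "Analysis of maternal plasma/urine/hair magnesium and vanadium levels in preeclampsia". Section 3 (Outcome Measures) sets three comparisons, and Section 4 (Endpoints of the study) repeats them:

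- Primary: "The primary outcome in these analyses will be compare magnesium and vanadium levels in LOPE group and the control groups".
- Secondary: "The secondary outcome will be compare the magnesium and vanadium levels in mild LOPE group and severity LOPE group".
- Tertiary: "Tertiary outcome will be compare the magnesium and vanadium levels in SGA group and non-SGA group".

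Section 3 then gives the document's only sampling sentence, "Venous blood sampled from the antecubital veins for measuring plasma concentration of cadmium, lead and vanadium levels", and its only assay sentence, "The three metals (cadmium, lead and vanadium) were measured using inductively coupled plasma-mass spectrometry".

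The one other statement about measurement is in Section 5 (Limitations and strengths). It begins "These metals will be measured blood, urine and" and goes on to hair. It names neither a metal nor a method.

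Section 1 gives the groups as "70 late-onset preeclampsia patients as a study group, 70 participants with normal pregnancies as control pregnant group and 70 participants with healthy volunteer women".

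**The concern.** The metals to be compared and the metals to be measured are different lists. Magnesium is in every outcome but in neither procedure sentence. Cadmium and lead are in both procedure sentences but in no outcome.

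Two things are at stake. First, a laboratory working from Section 3 as written would report cadmium, lead and vanadium in plasma, and no magnesium. Half of the primary outcome would then lack its plasma values. Second, even if the laboratory does run magnesium, the plan states no method for it. It also leaves cadmium and lead without a status, so a reader could not later tell whether results for them had been planned or were exploratory.

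**Working it through.** The plan states no figure on this point, so there is none to reproduce. The check sets the passages side by side and then counts.

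**Metals named in each place**

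| Place | Mg | V | Cd | Pb |
|---|---|---|---|---|
| Title | yes | yes | no | no |
| Primary outcome (Sections 3 and 4) | yes | yes | no | no |
| Secondary outcome (Sections 3 and 4) | yes | yes | no | no |
| Tertiary outcome (Sections 3 and 4) | yes | yes | no | no |
| Blood-sampling sentence (Section 3) | no | yes | yes | yes |
| Assay sentence (Section 3) | no | yes | yes | yes |
| Section 5 | not named | not named | not named | not named |

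**Overlap of the two lists**

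- Outcomes: {Mg, V}. Procedure: {Cd, Pb, V}. In both: {V}.
- Outcome metals without a stated assay: {Mg}, 1 of 2.
- Metals listed for assay that belong to no outcome: {Cd, Pb}, 2 of 3.

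**Women without plasma magnesium if Section 3 is followed literally**

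- Primary: 70 preeclampsia + 70 pregnant controls + 70 non-pregnant controls = 210.
- Secondary: the 70 preeclampsia women.
- Tertiary: 70 if small-for-gestational-age (SGA) status is compared within preeclampsia only, or 70 + 70 = 140 if among all pregnant women. This range is an assumption, because the document does not say which women enter the comparison.

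**How far the plasma gap reaches**

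The title names three matrices: plasma, urine and hair. Crossing metals, matrices and outcomes gives 2 x 3 x 3 = 18 combinations. Plasma magnesium accounts for 1 x 1 x 3 = 3 of them. Within plasma alone it is 3 of 2 x 3 = 6. The sampling sentence covers plasma only. For urine and hair the document gives no list of metals, so the other 6 magnesium combinations (1 x 2 x 3) are unspecified; they are not shown to be lost.

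**Could the text be read so that the conflict disappears?**

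- Both Section 3 sentences are complete, with no gap or redaction, and they agree with each other.
- The document has no amendment log, so neither list is marked as superseded.
- If cadmium and lead were extra metals, that would explain why they appear. It would not explain why magnesium is absent from both sentences.
- The document refers to no laboratory manual that might hold a different list.

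The sample-size statement in Section 2 uses a standardised effect and names no metal, so it is not affected.

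**The case against.** The strongest reply is that the intention is plain. The title and every outcome name magnesium and vanadium, the Section 3 list looks like text carried over from elsewhere, and what the laboratory actually runs is not in the document. On this view the defect is a wording error with no proven harm. That stands as far as harm is concerned: a copying error is plausible, and the document does not show that magnesium will go unmeasured. It does not remove the conflict, because the faulty list is the only assay specification in the plan and it appears twice.

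Section 5 offers a second reply. The metals last named before it, in Section 4, are magnesium and vanadium, so its unnamed metals could be those two. In that case the document does say that magnesium will be measured in blood, urine and hair. The other reading is also open: apart from Section 5, the word metals is applied only to the Section 3 trio. The reference is ambiguous, and on either reading no method is given for magnesium.

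A reader might infer more, namely that the magnesium half of the study would have no data at all. The document does not support that. It would hold only if the three-metal list also governed urine and hair, and the text does not say so.

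**Conclusion.** The inconsistency is certain from the text and must be fixed, because it concerns one of the two metals in the primary outcome. The size of the defect is 1 of 2 outcome metals without a stated assay, and 2 of 3 assayed metals without an outcome. The loss of plasma magnesium for 210 women is conditional on Section 3 being carried out as written; it is not a prediction of what the laboratory will do. The vanadium comparisons are unaffected. The absence of a described procedure for urine and hair is a separate and lesser gap.

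**What to change.** 1. Confirm with the laboratory which metals are on the ICP-MS panel.
2. Correct both Section 3 sentences so that the assayed metals are magnesium and vanadium, matching the title and the three outcomes.
3. Delete cadmium and lead, or state that they are exploratory and outside the primary, secondary and tertiary outcomes.
4. If magnesium is not on the panel, add it. If the outcomes are to be changed instead, that alters the primary outcome, so it needs a dated, justified amendment before the data are analysed.

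**Cost.** If magnesium is already on the panel: two sentences and one laboratory check. If it is not: up to 3 x 70 = 210 added measurements for plasma alone, or up to 3 x 210 = 630 across plasma, urine and hair. Both figures assume one sample per matrix per woman, because the number of samples is not stated. No extra participants are needed.
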